1.0 Research Design

1.1 Purpose/Specific Aims

A. Objectives

- 1) To assess the effect of a high-fiber supplement (HFS) diet on gut microbiota and immune cells in Multiple Sclerosis (MS).
- 2) To identify biomarkers of disease exacerbation in relapsing remitting (RR)-MS.

B. Hypotheses / Research Question(s)

Increase in consumption of high-fiber diet could be beneficial for neurodegenerative diseases including MS. Recently, our collaborator, [name], developed a HFS and his study suggests an association between intake of HFS and reduced gut dysbiosis and the growth of SCFA-producing gut bacteria in Type-II diabetes mellitus (T2DM). Since MS is associated with gut dysbiosis and decreased production of SCFA, we will investigate the effect of HFS on MS associated gut dysbiosis. Currently, there is no patent present, but the submission of this patent is in process.

1.2 Research Significance

It has been suggested that dysbiosis of gut commensal bacteria is associated with increased risk of autoimmune diseases including MS. However, there is no viable intervention available to correct dysbiosis. Since, intake of HFS is associated with the growth of healthy bacteria in the gut, we propose to investigate the effect of HFS on the growth of SCFA-producing gut bacteria and development of regulatory cells in MS. If this study is successful, consumption of HFS could be beneficial therapeutic supplement to disease modifying drugs in halting MS progression and would justify the launch of a clinical trial with this HFS.

Additionally, it is necessary to find a non-invasive biomarker for gut dysbiosis-mediated CNS autoimmunity in MS. Since we found that fecal Lcn-2 is a biomarker of gut dysbiosis-mediated CNS autoimmunity in MS animal models, we will investigate the association of fecal Lcn-2 levels with disease activity in RR-MS. If this result is positive, fecal Lcn-2 could become one of the biomarkers for disease exacerbation in RR-MS.

1.3 Research Design and Methods

RR-MS patients will be recruited from the Robert Wood Johnson Center for MS under the direction of [name]. The patients will be asked to participate in the study during their regular clinical visit to the MS Center.

Inclusion criteria includes patients aged 21-65 Relapsing Remitting Multiple Sclerosis (RRMS) who met the 2017 McDonald criteria.

The first group (**Group A**) of MS patients (**n=25**) will receive a dietary fiber supplementation. They will consume 60 g/day of HFS for 12 weeks (High-fiber supplement group, Group-A). The supplement consists of a mixture of soluble fibers (from inulin and fibersol-2) and insoluble fibers (from oat bran, corn bran, wheat bran and sorghum bran) and it will be consumed as a drink.

The second group of MS patients (**Group B**) (**n=25**) will not consume any high fiber supplement.

The first group (**Group C**) of healthy volunteers (**n=25**) will receive a dietary fiber supplementation. They will consume 60 g/day of HFS for 12 weeks. Healthy volunteers will not have MS.

The second group (**Group D**) of healthy volunteers (**n=25**) will not consume any high fiber supplement.

For Groups A, B, C & D stool, and serum samples will be collected at 3 time points (baseline; Week 8; & Week 12).

Group E (n=25) will consist of 25 subjects with MS who experience an MS flare up.

These 25 subjects can be those participants with MS who are already part of the above study (Group A or B) and consent to 2 extra blood and 2 extra fecal samples collected at the time of the acute flare up and upon resolution of symptoms.

Screening visits will typically take place during routine MS follow up visit at the Robert Wood Johnson Center for MS. During this time, eligibility will be reviewed, and consent will be obtained once the patient has had time to review the study, have questions answered, and agree to participate. During this screening visit, details regarding the patients MS history, food allergies/intolerances, medical history, and medications will be recorded. Eligible participants will be asked to provide blood and stool samples for baseline assessment.

A. Research Procedures

During the baseline visit, all MS patients and HDs will provide a blood and stool sample. For MS patients and HDs who are in the HFS group, they will be provided with supplies and instructions to take the supplement (Appendix 5). All the participants will be provided with stool kits and instruction on stool collection. Stool samples will be collected at home and transported to the laboratory by the participant in Piscataway for analysis.

Group A and Group C: MS patients in Group A and HDs in Group C will consume supplement orally as a drink two times a day to ensure fiber intake of 60 g/day for 12 weeks (High-fiber supplement group, Group A), as shown in [name] T2DM study (1). Participants will gradually increase the dosage of supplement over several days to mitigate the potential tolerability issues,

starting with daily consumption of 30g/day for first 5 days and then increasing to targeted daily consumption of 60g/day.

A member of the research team will follow up by phone at the end of the first week to check for compliance and adverse effects and then every month thereafter (Appendix 6). Patients will receive the fiber supplement in individual sachet (30g/sachet) by mail every two weeks, and they will be asked to return any unused supplement in their next study visit. Since the risks of study drug on embryofetal development are unknown, participants in Group A and Group C will be required to use contraception methods. Please refer section 5 special considerations for more details.

At baseline, Week 8 and week 12, 6 samples (3 blood and 3 fecal sample) will be collected from each subject.

All MS patients will be followed prospectively, and one more blood and one more fecal sample will be collected during relapse (before steroid treatment) and upon symptom resolution, and examined for intestinal inflammation, permeability, and microbial composition. The concentration of intestinal inflammation biomarkers in feces including Lcn-2, Calprotectin, and Lactoferrin, and a biomarker for intestinal permeability, serum zonulin, will be measured by ELISA assay.

As a control we will also analyze these biomarkers in the fecal samples isolated from healthy donors (n=25) in **Group C** and **Group D**. Healthy donors will be asked to provide 3 blood and 3 stool samples over the course of 12 weeks (baseline, week 8, and week 12).

Group E will consist of 25 subjects with MS who experience an MS flare up.

These 25 subjects will be those participants with MS who are already part of the above study (Group A or B) and consent to 2 extra blood and 2 extra fecal samples collected at the time of the acute flare up and upon resolution of symptoms. These subjects will be asked to sign a separate consent form agreeing to be part of the MS flare up group (n=25). Since around 50% of RRMS patients relapse at least once per year, we anticipate recruiting 25 relapsing RRMS patients from Group A and B in 1 years (2). RRMS flare up and resolution will be determined by [name].

Table-1. Schedule of specimen collection

Screening/Baseline assessment	8 weeks post HFS	12 weeks post HFS	Unscheduled visit at MS Relapse	Unscheduled visit at MS remission
MS history Medical history Medication history Food Allergy Consent Blood draw* Fecal collection*	Blood draw Fecal collection	Blood draw Fecal collection	Blood draw** Fecal collection**	Blood draw Fecal collection

--	--	--	--

*Sample collection will be done on the day of screening or before high fiber supplement.

** Sample collection will be done at MS relapse before steroid treatment.

Sample collection:

1. Stool Sample: Subjects will be asked to collect a single-stool sample without any laxative or dietary restrictions using a sample collection kit (Appendix 1). The collected stool sample will be brought to the MS research laboratory by the participants. If participants cannot bring the stool sample to the MS research laboratory, our lab staff will pick up the stool sample. The stool sample will be examined for the composition of gut bacteria. The stool sample will also be transplanted into an animal model of MS and examined for the development of experimental autoimmune encephalomyelitis (EAE).

2. Blood Draw: All participants will visit RWJ MS center to provide a blood specimen. Each subject will have a blood draw (80ml – about 5 tablespoons) as shown in Table-1. The immune cells will be isolated from each blood specimen and the presence of pathogenic and regulatory immune cells will be analyzed.

*NOTE: It is requested that all blood work be fasting. Nothing to eat or drink 10-12 hours before blood draw. Subjects may have water &/or black coffee /tea.

Fasting is very important to check the levels of short-chain fatty acid in the serum.

B. Experiment

1. Examine the effect of HFS on production of SCFA, intestinal microbial composition, and intestinal permeability

Multiple sclerosis is associated with gut dysbiosis. Notably, gut dysbiosis in MS is associated with the loss of bacterial taxa involved in fermentation of dietary fiber and the production of SCFA (3-5). Since SCFA can promote the differentiation of Foxp3Tregs, a decrease in SCFA-producing bacteria in gut microbiota would be a risk factor for MS. Recently, our collaborator, [name] at our institution, developed a HFS. His recent study suggests an association between intake of HFS and reduced gut dysbiosis and increased abundance of short chain fatty acid (SCFA)-producing gut bacteria in T2DM (1). Since increase in SCFA-producing bacteria may be beneficial for inflammatory diseases including MS, we will investigate whether HFS can promote the growth of SCFA-producing bacteria in MS patients and promote the development of regulatory immune cells.

The stool and serum will be collected at 3 time points (pre-HFS; 8 and 12 weeks after consumption of HFS) from MS patients. Similar samples will be obtained from the HFS treated and non-treated control group at similar time points. Fecal DNA will be extracted using the QIAamp PowerFecal DNA Kit (QIAGEN). DNA quality and quantity will be measured using the NanoDrop™ One microvolume UV-Vis Spectrophotometer (Thermofisher) and Qubit 1x dsDNA HS assay (ThermoFisher) respectively. Gut bacterial composition will be examined by 16S rRNA gene sequencing using the Ion GeneStudio S5 (Thermofisher) in [name] lab. QIIME 2 will be used to analyze the sequencing data to identify the amplicon sequence variants (ASVs). ASVs will then be grouped into guilds based on their abundance correlations. Biomarkers and microbiome-based prediction models will be explored at both the ASV and guild level using statistical methods such as Random Forest and Partial Least Squares regression models. Samples of potential significance will be shortlisted for subsequent whole genome metagenomic sequencing. Concentration of fecal and serum SCFAs will be measured by Rutgers metabolomics core facility. Since Vitamin-D (Vit-D) is one of the most important nutrients that affect immune modulation (6, 7), we will also measure serum Vit-D levels.

Next, we will assess the effect of HFS on intestinal permeability. MS is associated with gut dysbiosis and intestinal permeability (3-5, 8). Therefore, we will examine gut intestinal permeability (IP) by measuring the serum levels of zonulin, which is a biomarker of IP (9), using a zonulin ELISA kit

PBMCs will be stained with anti-CD3, CD4, Foxp3, CD25, and CD127 mAbs and CD3+CD4+CD25+CD127lo Foxp3+population in a CD4 T cell compartment will be analyzed by flow cytometry using Kaluza software. Development of Th1, Th17, and Th-GM-CSF will be analyzed by flow cytometry with anti-CD4, CD3, IFN- γ , IL-17A, and GM-CSF mAbs. Since low expression of E3 ubiquitin ligase genes is associated with MS disease exacerbation, we will examine the expression of E3 ubiquitin ligase genes. Naïve and memory/effector T cells will be isolated from PBMCs by naïve-memory isolation MACS beads and expression of CBLB, ITCH, and GRAIL genes will be examined by q-PCR. Since PD-1:PD-L1 signaling is important to prevent CNS autoimmunity and a fiber rich vegetarian diet can promote PD1:PD-L1 signaling (10-12), we will also study the expression of PD-1 on CD4+ T cells and PD-L1 on monocytes/macrophage and DCs using flow cytometry. PBMCs will be stained with anti-CD4, CD3, CD11c, CD11b, CD14, PD-1 and PD-L1 mAbs, and CD3+CD4+PD-1+ population in CD4+ T cells; and CD11c+PD-L1+ (DC), CD11b+PD-L1+ (macrophage) and CD14+PD-L1+ (monocyte) cell compartment will be analyzed by flow cytometry. To examine the production of inflammatory cytokines in antigen presenting cells, DCs and macrophages isolated from PBMCs will be cultured in the presence or absence of exogenous lipopolysaccharides (LPS) for 3 days and production of IL-6, IL-12, IL-1, and IL-23 will be examined by ELISA.

2. Examine the effect of HFS-induced gut microbiota on EAE in a 3A6/DR2a MS animal model:

Human microbiota-associated (HMA) mice, in which the human gut microbiota is established in germ-free mice via fecal transplantation, has been used for evaluation of pathogenic and beneficial role of gut microbiota in human health (13). Several studies have shown the usefulness of this model that can mimic the pathophysiology of human diseases such as asthma, pregnancy-induced adiposity, and obesity (14-18).

We will establish a germfree 3A6/DR2a at Taconic Inc. and expand them in our facility. Since 3A6/DR2a mice are prone to develop EAE between the age of 6 to 10 week-old, 4 week-old mice will be used for creating HMA-3A6/DR2a mice. Fecal samples will be collected from HDs and MS patients on regular diet and HFS at 3 time points (pre-treatment; 8, and 12 weeks after treatment) and the fecal sample will be transplanted into 3A6/DR2a mice (20 mice in each group). Each fecal sample (0.5 g) will be diluted in 25 mL of a sterile Ringer working buffer in an anaerobic chamber. The fecal material will allowed to settle by gravity and the clarified supernatant will be mixed with an equal volume of 20% (w/v) skimmed milk (Oxoid). Mice will be orally administered with 100 μ L of fecal suspension inoculum. The development of spontaneous EAE will be monitored until the age of 20 weeks.

We will also assess the microbial composition and intestinal permeability in the transplanted mice. The fecal samples will be collected every 7 days post fecal transplantation and gut microbiota composition will be examined by sequencing of V4 region of 16S rRNA gene using iontorrent sequencer (Thermofisher) as described earlier. To measure the intestinal permeability, the transplanted mice will be administered with 150 μ l of FITC dextran by oral gavage and appearance of FITC-dextran in the blood will be measured 4 h after oral inoculation. The serum FITC-dextran concentration will be measured using a fluorimeter. Since serum levels of endotoxin is also a biomarker of intestinal permeability, serum endotoxin activity will be measured using PierceTM Limulus Amebocyte Lysate (LAL) Chromogenic Endotoxin Quantitation Kit.

We will next assess the development of pathogenic and regulatory immune cells. Three mice in each group will be euthanized at the age of 6-10 week-old and development of pathogenic Th1, Th17, and Th-GMCSF cells in intestinal lamina propria, mesenteric lymph nodes, spleen, and CNS will be examined by flow cytometry with anti-CD4, V β 5.1, CD3, IFN- γ , IL-17A, GM-CSF mAbs. Development of Foxp3 Tregs will be examined by flow cytometry with anti-Foxp3, GITR, CD4, and V β 5.1 mAbs. Based on our earlier findings (19), down-regulation of E3 ubiquitin ligase, CBLB and ITCH, will be examined by q-PCR.

We will also examine the development of inducible EAE in C57BL/6 mice transplanted with fecal samples. Germ-free C57BL/6 mice will be purchased from Taconic Inc. and expanded for the experiment. The fecal samples will be collected from regular diet- and HFS-treated HDs and MS patients as described above and transplanted into the germ-free C57BL/6 mice (10 in each group). The transplanted mice (7-9 week-old) will be immunized with MOG35-55 at 200 ug/mouse and injection with pertussis toxin at 100 ng/mouse. Development of EAE will be examined for 40 days. Demyelination and axonal loss in the brain and spinal cord will be examined by immunohistology

with anti-MBP and -Neurofilament Abs, respectively. Microbial composition, intestinal permeability, and development of Th-1, Th-17, Th-GMCSF and Foxp3 Tregs will be examined as described above.

3. Explore biomarkers of MS-associated gut dysbiosis and response to HFS:

RR-MS and healthy donors (21-55 year-old) from RWJ MS Centers will be asked to participate in this study according to institutional IRB guidelines. In this study, fecal and blood samples will be collected from RR-MS patients during relapse (before steroid treatment) and later during remission and examined for intestinal inflammation, permeability and microbial composition. We will enroll 25 patients based on sample size calculation using related previous studies with a statistical power of 80% (8, 20). The fecal samples (200 mg) will be dissolved in 0.5 ml PBS containing proteinase inhibitor and the supernatant will be collected. The concentration of intestinal inflammation biomarkers including Lcn-2, Calprotectin, and Lactoferrin, and a biomarker for intestinal permeability, serum zonulin, will be measured by ELISA assay. We will examine the association between increase in intestinal inflammation/permeability and disease activation.

The fecal samples collected from HFS-treated and un-treated MS patients at the 3 time points described in Aim-1, will be analyzed for intestinal inflammation and permeability as described above. We will simultaneously examine the microbial composition in the fecal samples as described in Aim-1 to determine if an association between MS relapse and gut dysbiosis exists.

C. Study Duration

Subjects participation will be 12-week period.

Study Timetable:

Upon IRB approval-Sept. 2023 Collection of blood and fecal specimens

Sept. 2021-Sept. 2023 Analysis of blood and fecal specimens

Sept. 2021-Aug. 2023 Fecal transplantation in germ free mice and analysis for EAE

D. Endpoints

The primary endpoint will be detection of effect of HFS on intestinal microbial composition, intestinal permeability, production of SCFA, intestinal permeability, and immune cells in 25 MS patients between before and after intake of high-fiber supplement.

The secondary endpoint will be detection of biomarkers for intestinal inflammation-associated disease exacerbation in 25 MS patients.

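### The Group E size of 25 relapse cases is the expected one-year count with no margin, the relapse follow-up period is not reconciled across sections, and the healthy reference can include fiber-treated volunteers

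*Combined protocol and SAP*

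**What the plan says.** Section 1.3 A forms Group E from MS patients in Groups A and B who relapse. Taking about 50% as relapsing at least once a year, it says "we anticipate recruiting 25 relapsing RRMS patients from Group A and B in 1 years". Section 4.3 A sets the pool at 50 MS patients. Section 1.3 B.3 attaches 80% power to 25 patients, and section 1.3 D defines the secondary endpoint in 25.

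A relapse has to pass several steps to count. On consent: "These subjects will be asked to sign a separate consent form agreeing to be part of the MS flare up group". On the first sample: "Sample collection will be done at MS relapse before steroid treatment". Section 1.8 A allows 1 to 6 months for the remission sample. No allowance for losses at these steps is given.

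Timing appears in several places:
- Section 1.3 C: "Subjects participation will be 12-week period".
- Section 1.3 A: "All MS patients will be followed prospectively", with no duration, alongside the one-year horizon quoted above.
- Section 1.8 A: flares both within the study and after its completion are eligible, with no end date.
- Sections 1.3 C and 1.10: specimen collection runs from an undated IRB approval to September 2023.
- Section 4.3 C: recruiting the 50 MS patients takes one year.

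Section 1.3 B.3 gives an age range for this aim: "RR-MS and healthy donors (21-55 year-old) from RWJ MS Centers will be asked to participate in this study". Sections 1.3 and 4.1 C enrol ages 21 to 65.

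For the control, section 1.3 A says "we will also analyze these biomarkers in the fecal samples isolated from healthy donors (n=25) in" Groups C and D. Group C takes the supplement.

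**The concern.** A target equal to the expected count is missed almost half the time even when nothing goes wrong, and any loss at consent, sampling or follow-up lowers the odds further. Whether a longer period makes up for this depends on which timing statement governs, and the protocol does not say. At stake is the stated size of the secondary endpoint and the 80% power attached to it.

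The second issue affects the same comparison. If week 8 and week 12 samples from Group C enter the healthy reference, some controls have been exposed to an intervention that the study expects to change these gut markers. The relapse-versus-healthy difference would then partly reflect the supplement.

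**Working it through.** **Inputs from the protocol.** Pool 50 (section 4.3 A); relapse probability about 0.50 per year (1.3 A); target 25 (1.3 A, 1.3 B.3, 1.3 D); accrual one year (4.3 C); reference size 20 (1.5); stated power 80% (1.3 B.3).

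**Assumptions.** Capture share c of 100%, 90%, 80% or 70%. For periods other than one year, a constant relapse rate common to all patients, calibrated to 50% at one year (hazard ln 2 per year).

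**Step 1: the plan's figure.** 50 × 0.50 = 25. It reproduces.

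**Step 2: one full year per patient.** The number of cases is Binomial(50, p). If a loss removes the patient (refused consent), p = 0.5c. If it removes one relapse and a later one can still count (no sample before steroids), p = 1 − 0.5^c. The real mix is unknown, so the two models bracket the answer.

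| Capture | Expected cases (per patient / per relapse) | P(≥25) | P(≥20) |
|---|---|---|---|
| 100% | 25 / 25 | 56% | 94% |
| 90% | 22.5 / 23.2 | 28% / 36% | 80% / 85% |
| 80% | 20 / 21.3 | 10% / 18% | 55% / 69% |
| 70% | 17.5 / 19.2 | 2% / 6% | 27% / 46% |

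The word around matters too: at perfect capture, P(≥25) is 28% if the yearly rate is 45% and 80% if it is 55%.

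**Step 3: other periods, perfect capture.**
- Uniform accrual over one year, capture closing with accrual: p = 1 − (1 − 0.5)/ln 2 = 0.279; 50p = 13.9 cases; P(≥25) below 0.1%.
- The same accrual plus one further year (assumed): p = 1 − (0.5 − 0.25)/ln 2 = 0.639; 50p = 32.0 cases; P(≥25) = 98%.

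In the longer window, at 90%, 80% and 70% capture, P(≥25) is 89%, 62% and 27% with loss per patient and 94%, 84% and 62% with loss per relapse.

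**Step 4: complete pairs.** I read the 1 to 6 months as time after the relapse. In the longer window at perfect capture, a relapse at least 1 month before closure gives p = 0.618, or 30.9 pairs. At least 6 months before closure gives p = 0.490, or 24.5 pairs.

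**Step 5: period needed for an 80% chance of 25 cases.** Binomial(50, p) needs a captured p of 0.549. Solving c(1 − 0.5^t) = 0.549 (per patient) gives t = 1.36 years at 90% capture and 1.67 at 80%. Solving 1 − 0.5^(ct) = 0.549 (per relapse) gives 1.28 and 1.44.

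**Step 6: what a shortfall costs.** The protocol gives no effect size or SD for this aim, so power is conditional on its own claim. If 25 against 25 has 80% power (two-sample t test, two-sided 5%), the standardised difference is 0.809. Power is then 72% for 18 against 25, 75% for 20 against 25, 83% for 18 against 50 and 85% for 20 against 50. If instead 20 against 20 has 80% (difference 0.909), 18 to 20 cases have 82% to 84% against 25 and 90% to 92% against 50.

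**Step 7: healthy reference.** A footnote to Table-1 says of baseline collection: "Sample collection will be done on the day of screening or before high fiber supplement". So baseline samples from all 50 volunteers in Groups C and D are unexposed. Later Group C samples are not, and section 1.3 A does not exclude them.

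**The case against.** The strongest reply is that the 25 is a forecast for a secondary endpoint and that the protocol is not silent on timing: it gives a one-year horizon, prospective follow-up and capture of flares after completion. A window somewhat beyond one year would usually deliver 25. That stands in part. The defect is that the statements are not reconciled, and they lead to expected counts from about 14 to 32.

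A second reply is that charging every loss to the patient is too pessimistic, since nothing limits capture to the first relapse. That is correct, and the per-relapse figures are shown for this reason. They still leave P(≥25) at 36% or less for one year at 90% capture or below.

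A third reply is that 20 cases may be enough, as section 1.5 says of its inflammatory bowel disease source, and that using 50 healthy baselines keeps power at 80% or more with 18 to 20 cases if the stated 80% holds. This also stands and limits the consequence.

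On the control, sections 1.5 and 1.6 together favor reading n=25 as 25 healthy volunteers in total. That does not settle which samples are used.

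A reader might infer that only relapses within the 12-week participation count, which would give about 7 cases (50 × (1 − 0.5^(12/52)) = 7.4). The protocol does not support this: 12 weeks fits the scheduled phase, and section 1.8 A explicitly accepts later flares.

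**Conclusion.** The point holds as one of attainability and unreconciled timing. There is no arithmetic error. With one year per patient, expected cases are about 18 to 23 at 70% to 90% capture, and the chance of reaching 25 is 56% at best and 2% to 36% with losses. These figures rest on the protocol's 50%, on assumed capture shares and, for the per-relapse model and other periods, on a constant common rate.

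The consequence is moderate. It would be tempting to conclude that the relapse aim is underpowered. The documents do not show that: without an effect size or SD the 80% can be neither confirmed nor refuted, and taken at face value 18 to 20 cases keep 83% to 85% against 50 baselines, though 72% to 75% against 25.

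The healthy reference is a separate defect and needs no assumption: as written, supplement-treated volunteers can enter the control.

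**What to change.** **1. Group E size and period.** Reconcile sections 1.3 A, 1.3 C, 1.8 A, 1.10 and 4.3 C into one relapse follow-up period per patient, with a last relapse date that leaves room for the remission sample. Restate expected cases and complete pairs under a stated capture assumption. Then choose one of two routes:
- Restate the size, for example as 20, which one year each reaches with 80% to 85% probability at 90% capture.
- Keep 25 and state a period that supports it. For an 80% chance this is about 1.3 to 1.4 years each at 90% capture, or 1.4 to 1.7 at 80%, under a constant rate. It is longer if risk varies between patients.

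State whether ages 21 to 55 or 21 to 65 apply to this aim, since the narrower range could reduce the pool below 50.

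**2. Healthy reference.** For relapse versus healthy, use only the baseline samples of Groups C and D taken before the supplement (up to 50 volunteers), and account in the analysis for supplement exposure among relapsing Group A patients.

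**Cost.** Protocol wording, and either a less favorable stated number or longer relapse follow-up of the same patients. If n=25 means 25 volunteers in total, up to 25 more assays are needed on samples already collected. No patients or scheduled samples are added. The week 8 and week 12 healthy samples drop out of this one comparison.

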4.0 Subject Considerations

4.1 Subject Selection and Enrollment Considerations

A. Method to Identify Potential Subjects

2017 McDonald criteria will be used to select relapsing remitting MS patients. Age and sex matched healthy donors will be recruited from Rutgers students/staff volunteers or New Jersey local resident using e-mail with study flyers.

B. Recruitment Details

The study will recruit both participants who have MS and Healthy Volunteers. Subjects will be recruited at RWJ Center for Multiple Sclerosis ambulatory clinic.

Patients will be recruited from the outpatient neurology clinic of the Rutgers Robert Wood Johnson Center for MS. The patients will be asked to participate in the study during their regular clinical visit to RWJ MS Center. Only if the patient agrees to participate and meets enrollment criteria will they be enrolled in the study.

Healthy volunteers will be recruited from Rutgers students/staff volunteers or New Jersey local resident. There will be no undue influence on students / staff. Participation is completely voluntary. The healthy donor recruitment flyer will be emailed to students / staff. Those who are interested can reach out to obtain further information and be screened for eligibility.

C. Subject Screening

Subjects will be screened by [name] at RWJ MS center based on inclusion and exclusion criteria laid out in this study.

▪ Inclusion Criteria

1. Patients who meet 2017 McDonald criteria for RRMS.
2. Both males and females (age 21-65 year old).
3. Newly diagnosed and RRMS patients who are taking non-oral MS medications like interferon, Copaxone and Tysabri.
4. RRMS patients who refuse to take MS medications but are interested in other interventions.
5. Healthy volunteers without any chronic inflammatory or autoimmune diseases will be included in the study as controls.

Exclusion Criteria

1. Primary or secondary progressive MS.
2. Patients with autoimmune comorbidities.
3. Having received prior chemotherapy.
6. Pregnant women.
7. Cognitively impaired.
8. Antibiotic use within last 6 months.
9. Probiotic use within the last 2 months.

10. Self-reported allergy or intolerance to any ingredients in the fiber supplement.
110. Self-reported or diagnosed gastrointestinal disorders (such as; Irritable Bowel Syndrome, Diverticulitis, Chron's Disease)
121. Active or history of malignant tumors

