4.3 Number of Subjects

A. Total Number of Subjects

50 MS patients and 50 healthy donors will be enrolled in this study. Please refer to section “1.5 Sample Size Justification” for calculation regarding sample size.

B. Total Number of Subjects If Multicenter Study – N/A

C. Feasibility

RWJ MS Center evaluates enough newly diagnosed MS patients every year to be able to recruit 50 MS patients for the study over 1 years. 50 healthy volunteers will be recruited from Rutgers students/staff and New Jersey local resident..

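### The healthy comparator for the relapse-versus-healthy biomarker contrast is not consistently defined: age range, number, donor source, visit and supplement status all need to be settled

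*Combined protocol and SAP*

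**What the plan says.** - **Contrast.** Section 1.6 gives Experiment 3 two groups, MS patients in relapse and healthy volunteers, with intestinal inflammation and permeability as outcomes.
- **Age.** Section 1.3 B.3: "RR-MS and healthy donors (21-55 year-old) from RWJ MS Centers will be asked to participate in this study". The opening of section 1.3 says "Inclusion criteria includes patients aged 21-65 Relapsing Remitting Multiple Sclerosis (RRMS", and the inclusion list in section 4.1 C says "Both males and females (age 21-65 year old". That list also admits the healthy volunteers. Sections 1.3 A and 1.8 draw the relapse group (Group E) from enrolled MS participants and set no separate age limit.
- **Number.** Section 1.3 A: "As a control we will also analyze these biomarkers in the fecal samples isolated from healthy donors (n=25) in" Groups C and D. Section 1.3 puts 25 donors in each of those groups, and section 4.3 A says "50 MS patients and 50 healthy donors will be enrolled in this study". Section 1.5 proposes 25 per group for Aim 3.
- **Source.** Section 1.3 B.3 places the donors at the MS centers. Section 4.1 B introduces patients and volunteers together and then says "Subjects will be recruited at RWJ Center for Multiple Sclerosis ambulatory clinic". Section 4.1 A says "Age and sex matched healthy donors will be recruited from Rutgers students/staff volunteers or New Jersey local resident", and the volunteer paragraph of 4.1 B and section 4.3 C agree with that.
- **HFS exposure and visit.** Group C takes HFS for 12 weeks and Group D does not. Both give samples at baseline, Week 8 and Week 12. A footnote to Table 1 puts the baseline sample before HFS. No section says which visit, or which HFS status, supplies the Experiment 3 control.

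**The concern.** A relapse-versus-healthy difference can be interpreted only if the reader knows who the healthy people were and what they had been exposed to. Three things are at stake.

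- **HFS in the control.** The study's premise is that HFS changes the gut, and section 1.4 C plans to examine its effect on intestinal inflammation. Group C samples from Week 8 or 12 would bring the tested intervention into the reference group.
- **Eligibility.** A relapsing patient aged 56-65 qualifies under section 4.1 and does not under section 1.3 B.3. Staff cannot follow both.
- **Choice after the fact.** With several possible control sets (one group or both, any of three visits, 25 or 50 people), the set could be chosen once the data are known. In the text available, section 6.1 on data analysis has a heading but no content that would settle it.

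**Working it through.** **1. The plan's own figure.** Sections 1.3 B.3 and 1.5 give 25 per group at 80% power. No mean difference or SD is stated for Aim 3, so 25 cannot be reproduced. It can only be inverted to show the difference it could detect.

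Inputs: 25 relapsers and 80% power (sections 1.3 B.3 and 1.5). The 5% type I error is stated in section 1.5 for the regulatory-cell calculation only. I assume that it carries over, is two-sided, and that SDs are equal.

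Formula (normal approximation): detectable difference in SD units = (1.960 + 0.842) × √(1/n1 + 1/n2). The last column uses the noncentral t.

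| Comparison | √(1/n1 + 1/n2) | Normal | Noncentral t |
|---|---|---|---|
| 20 v 20 (the cited IBD study's n=20, if per group) | 0.316 | 0.89 | 0.91 |
| 25 v 25 | 0.283 | 0.79 | 0.81 |
| 25 v 50 | 0.245 | 0.69 | 0.70 |

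Moving from 25 to 50 controls multiplies the standard error by 0.245/0.283 = 0.866, a fall of 13%.

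**2. Power over an assumed range of true differences (noncentral t).**

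| True difference (SD) | 25 v 25 | 25 v 50 |
|---|---|---|
| 0.5 | 41.0% | 52.2% |
| 0.6 | 54.7% | 67.6% |
| 0.7 | 67.9% | 80.5% |
| 0.8 | 79.1% | 89.7% |
| 1.0 | 93.4% | 98.1% |

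This gain exists only if 25 donors would otherwise be left out.

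**3. Effect of HFS on the contrast.** Let h be the mean change that HFS causes in a healthy donor's biomarker. The documents give no value. The contrast is relapse mean minus control mean.

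- Groups C and D pooled equally at Week 8 or Week 12: half the control samples are exposed, so the contrast moves by −h/2.
- Both groups pooled over all three visits: 2 of 6 group-visit sets are exposed, so it moves by −h/3.
- Baseline samples only: it moves by 0.

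On the patient side, let a share p of relapsers come from Group A with HFS exposure, and let g be the HFS effect in patients. The contrast then moves by +p × g whichever donors are used. Baseline controls therefore remove the control-side term and leave the patient-side term.

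**4. Age.** Section 1.3 B.3 applies 21-55 to both sides, and section 4.1 C has one list for both sides at 21-65. Each is internally even. Donors could be capped at 55 with patients running to 65 only if donors followed one section and patients the other, and no section states that combination. The documents give no age distribution, so the share of patients aged 56-65 cannot be calculated.

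**The case against.** The strongest reply is that these are drafting slips with little consequence.

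- **Matching.** A reader might infer that the comparison is not age-matched. The documents do not support that: section 4.1 A promises age and sex matching, and each age statement covers patients and donors alike. What stands is that the limits disagree and that no matching method or reference group is given.
- **Wasted controls.** A reader might infer that half the donors go unused. The phrase "in the fecal samples isolated from healthy donors (n=25) in" Groups C and D can equally mean 25 in each, and the summary in section 1.5 uses samples from 50 healthy controls for gut permeability. The loss is conditional.
- **Lost relapse cases.** A reader might infer that relapsing patients aged 56-65 will be turned away, or put a figure on them by spreading ages evenly over 21-65. Section 1.8 says that any enrolled MS participant with a flare will be asked to join Group E, and nothing supports an even spread.
- **Exposure.** Group C baseline samples precede HFS, so only its Week 8 and Week 12 samples are affected. This stands, and the remedy depends on it. It does not answer the absence of a named visit.
- **Source.** Screening and blood draws take place at the MS center, so the wording in 1.3 B.3 may be loose. That is plausible, but the text still needs correcting.
- **Reach.** The secondary endpoint is stated in 25 MS patients, and section 1.3 B.3 samples the same patients at relapse and remission. That contrast needs no healthy donors. This limits the point to the relapse-versus-healthy contrast.

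**Conclusion.** The concern holds as an inconsistent and incomplete definition of the healthy comparator, limited to the Experiment 3 relapse-versus-healthy contrast. The age ranges and donor sources conflict, the control number is ambiguous, and neither visit nor HFS status is fixed. HFS exposure matters most, because a permitted reading puts the tested intervention into the control samples. The resulting shift would be one third to one half of the HFS effect in the pooled cases shown above, and that effect is unknown.

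The precision at stake is 0.81 versus 0.70 SD at 80% power. This assumes 25 relapsers are obtained, a two-sided 5% test and equal SDs, and that only 25 donors would otherwise be used. If all 50 are already intended, the gain is nil and the remaining task is to say so. The documents do not show that the groups are unmatched.

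**What to change.** 1. Reconcile section 1.3 B.3 with the opening of section 1.3 and section 4.1 C, so that one age range applies to patients and donors. Reconcile the donor source across sections 1.3 B.3, 4.1 and 4.3 C.
2. Define the Experiment 3 control as the baseline, pre-HFS samples of all 50 healthy donors in Groups C and D, and state n=50 in sections 1.3 A, 1.5 and 1.6. Group D alone would also be free of HFS but gives 25 v 25.
3. Adjust the comparison for age and sex. Section 5.2 already collects donors' gender and date of birth and gives access to patients' medical records. State how the promised matching will be done.
4. Record each relapser's HFS exposure at relapse (none, current or past). Account for it by adjustment or by a sensitivity analysis limited to relapsers not exposed to HFS. That analysis will be imprecise: if 12 of 25 were unexposed (an assumption), the detectable difference against 50 donors would be 2.802 × √(1/12 + 1/50) = 0.90 SD by the normal approximation.

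The cost is text edits and a few covariates, with no new samples or visits.
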